13.5 Reporting Procedures

13.5.1 Participating Site Responsibilities

The PI (or delegated medically qualified doctor from the trial team) should sign and date the SAE CRF to acknowledge that he/she has performed the seriousness and causality assessments. Investigators should also report SAEs to their own health boards or trust in accordance with local practice. A completed SAE form for all events requiring immediate reporting should be submitted via email (or fax if email unavailable) to the CTR within 24 hours of knowledge of the event. A separate form must be used to report each event, irrespective of whether the events had the same date of onset. The participant will be identified only by trial number, month and year of birth, or year of birth and initials. The participant's name (or any other personal identifiers) should not be used on any correspondence. It is also required that sites respond to and clarify any queries raised on any reported SAEs and report any additional information as and when it becomes available through to the resolution of the event. Additionally, CTR companies may request additional information relating to any SAEs/SARs and the site should provide as much information as is available to them to resolve these queries.

Serious Adverse Event (SAE) email address:

[contact]

Serious Adverse Event (SAE) Fax number (Only use if email unavailable:

[name]

SAEs should be reported from time the participant goes into theatre, throughout the treatment period up to, and including seven postoperative days. SARs (such as long-term side effects of trial treatment under investigation) should continue to be reported until the end of follow up as defined in the protocol (page 77). SAEs should be graded using the NCI Common Terminology Criteria for Adverse Events (CTCAE) Version 5.0

(https://ctep.cancer.gov/protocoldevelopment/electronic_applications/docs/CTCAE_v5_Quick_Refe rence_5x7.pdf). CTR will code events using MedDRA Version 26.0.

An SAE form should contain at least the minimum information:

- Full participant trial number
- An AE/AR
- IMP or trial intervention
- A completed assessment of the seriousness, and causality as performed by the PI (or another appropriately medically qualified doctor registered on the delegation log)

If any of these details are missing, the site will be contacted, and the information must be provided by the site to the CTR within 24 hours. All other AEs should be reported on the CRF following the CRF procedure described in Section 13. If applicable, the PI should report any AE/SAE involving a device deficiency or occurring with a CE-marked device using the yellow card scheme (https://yellowcard.mhra.gov.uk/the-yellow-card-scheme/.

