4.2 Perineural Catheter use for Amputees

A PNC can be inserted at the time of lower limb amputation. As the tissues are divided, the sciatic nerve (for AKAs) or tibial nerve (for BKAs or TKAs) is identified. An epidural catheter is placed in the perineural space so that its tip lies as far as possible cranially from the amputated end. The catheter end is then removed through the skin away from the wound edge and secured. The overall process takes 5 to 10 minutes (38). It is then attached to a local anaesthetic infusion device which provides continuous infusion of local anaesthetic for the first 5 postoperative days. The PNC is removed on the

ward on the 5th postoperative day, unless earlier removal is required. The process of PNC placement and removal is almost identical to the placement and removal of surgical drains, which are often placed within the wound at the time of an amputation at the discretion of the operating surgeon.

The first use of a PNC for amputees was first described more than three decades ago (38). Malwer et al. (1991) demonstrated PNC usage to be associated with a significant reduction in postoperative opioid use in a series of case studies of upper and lower limb amputations (38). Our 2015 systematic review showed that no high-quality evidence exists regarding PNCs and pain relief in MLLA (39). We published an updated (2021) systematic review, including data from our feasibility trial (40). Ten studies (731 participants) were included; 350 participants receiving a PNC delivering local anaesthetic and 381 receiving no PNC or a PNC with placebo. We also searched ClinicalTrials.gov and the International Clinical Trials Registry Platform, finding no trials currently recruiting participants to a trial evaluating surgically placed PNC in MLLA (last search 10/08/21). Ongoing/future research that will complement PLACEMENT are trials evaluating ultrasound-guided peripheral nerve catheters/blocks preoperatively (41-43).

Our systematic review showed the following:

Acute pain

Meta-analysis of data from four studies; two RCTs (one of which was our feasibility trial) and two observational studies, including 462 participants, demonstrated that PNC use was associated with reduced acute pain (SMD: -0.30, 95% CI: -0.58 to -0.01). The Grading of Recommendations Assessment, Development and Evaluation (GRADE) quality of evidence was low.

Opioid use

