13.1 Definitions

Term	Definition
Adverse Event (AE)	Any untoward medical occurrence in a participant or clinical trial participant administered a medicinal product and which are not necessarily caused by or related to that product
Adverse Reaction (AR)	Any untoward and unintended response in a clinical trial participant to an investigational medicinal product which is related to any dose administered to that participant
Serious Adverse Event (SAE)	 Any adverse event that - Results in death Is life-threatening* Required hospitalisation or prolongation of existing hospitalisation** Results in persistent or significant disability or incapacity Consists of a congenital anomaly or birth defect Other medically important condition***
Serious Adverse Reactions (SARs)	Any SAE occurring in a clinical trial participant for which there is a reasonable possibility that it is related to the IMP at any dose administered.
Suspected Unexpected Serious Adverse Reactions (SUSARs)	A SAR, the nature and severity of which is not consistent with the Reference Safety Information (RSI) for the IMP. the definition of serious refers to an event in which the trial participant was at risk of

Table 3 Definitions of Adverse and Serious Adverse Events and Reactions

***Note:** The term 'life-threatening' in the definition of serious refers to an event in which the trial participant was at risk of death at the time of the event, or it is suspected that used or continued used of the product would result in the subject's death; it does not refer to an event which hypothetically might have caused death if it were more severe.

**** Note:** Hospitalisation is defined as an inpatient admission, regardless of the length of stay, even if the hospitalisation is a precautionary measure for continued observation. Pre-planned hospitalisation e.g., for pre-existing conditions which have not worsened, or elective procedures, does not constitute an SAE.

******* Note: other events that may not result in death, are not life-threatening, or do not require hospitalisation, may be considered as an SAE when, based upon appropriate medical judgement, the event may jeopardise the participant and may require medical or surgical intervention to prevent one of the outcomes listed above.

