13.2 Trial Specific SAE Reporting requirements

In addition to the SAE reporting requirements defined in Table 3, for the purposes of this trial the following events will also be considered SAEs and must be captured on the SAE form and reported to the CTR with 24 hours of knowledge of the event:

- Infection around PNC exit site
- Local anaesthetic toxicity reactions (see Section 11.6)

For the purposes of this trial the following events will **not** require reporting as SAEs:

• AEs as a result of surgical complications of CTCAE grades 1 and 2 as listed in the protocol (Table 6, page 64 - 65)

These should be completed in the participant's notes and on the relevant CRF page and forwarded

to the CTR in the normal timeframes for CRFs.

Pre-existing conditions should only be reported if they met the definitions for an SAE and if the condition worsens by at least one CTCAE grade.

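### Serious catheter-related events that start after day 7 have no clear reporting route, because SAE reporting closes on day 7 and the longer SAR window is defined by relation to the drug alone

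*Protocol*

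**What the plan says.** Section 13.5.1 sets the SAE window from entry to theatre "up to, and including seven postoperative days". It then gives a longer window to one class of event only: "SARs (such as long-term side effects of trial treatment under investigation) should continue to be reported until the end of follow up".

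Table 3 in Section 13.1 defines a SAR as an SAE with a "reasonable possibility that it is related to the IMP at any dose administered". Table 4 in Section 13.3 lists three local anaesthetics as the IMPs and shows catheter placement separately, as a procedure.

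Section 4.2 has the catheter taken out on the "ward on the 5th postoperative day, unless earlier removal is required".

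Three other places treat harm from the catheter as reportable in its own right:

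- Section 13.2 adds "Infection around PNC exit site" to the events that always count as SAEs and must reach the trials unit within 24 hours of being known.
- Section 13.3 assesses causality for the placement procedure as well as for the drugs.
- Table 7 in Section 13.4 gives catheter placement its own reference safety information.

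**The concern.** The intervention is a catheter plus a drug, but the only reporting window that outlasts the first week is worded for the drug. An exit-site infection that shows itself on day 10, for example, may owe nothing to the anaesthetic. It would fall after the SAE window and outside the Table 3 definition of a SAR.

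Safety oversight is what is at stake. Under Sections 13.5.2 to 13.7, SUSAR reporting, the annual safety update and the annual report to investigators all start from SARs, so an event that cannot be a SAR enters none of them. Section 4.2 justifies the trial partly by possible catheter-related harms, including direct nerve injury, and Table 6 lists failure to remove the catheter among the expected events. The protocol therefore regards these harms as worth watching. If sites read the definitions differently, the same late event will be reported at one hospital and not at another.

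**Working it through.** No sample size, power or error rate is involved. The check is a comparison of windows and definitions.

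**Windows**

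- Planned removal: day 5 (Section 4.2). Close of SAE reporting: day 7 (Section 13.5.1). Gap: 7 − 5 = 2 days.
- Surgical site infection is assessed at 30 days (Section 12.1.5). Counted from surgery, the SAE window covers 7 of 30 days (7/30 = 23%) and leaves 30 − 7 = 23 days, days 8 to 30, outside it.
- Counted from planned removal, the comparison is 2 days against 30 − 5 = 25 days.

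These figures compare a safety-reporting window with an outcome assessment. They show how early SAE reporting closes, not how many events are lost.

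**Can a late, catheter-only serious event be reported?** Take a serious event that starts after day 7 and is judged related to placement but not to the drug.

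1. As an SAE: Section 13.5.1 has closed the window. Section 13.2 names exit-site infection but gives it no window of its own, so the general limit appears to apply.
2. As a SAR: Table 3 requires a relation to the IMP, and Table 4 does not count placement as an IMP. On the literal wording, no.
3. Consistency: Section 13.4 assesses expectedness for SARs. The reference safety information that Table 7 gives to placement serves that purpose only if placement-related events can be SARs. Table 5 describes causality in terms of the trial or intervention, yet its decision column asks about the IMP alone. The definitions do not agree.

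**What else would record it?**

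- At 30 days: surgical site infection, delayed wound healing and residual limb surgery (Section 12.1.5).
- At discharge: Clavien-Dindo complications (Section 12.1.4), but not beyond.
- At 3 and 6 months: phantom and stump pain (Sections 12.2.1 and 12.2.2).
- At 6 months: wound healing, residual limb surgery, re-admissions and mortality (Section 12.2.2 and Table 2).
- Other adverse events go on the CRF with no stated end date, and device events go to the yellow card scheme where applicable (Section 13.5.1).

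None of the scheduled outcomes attributes the event to the catheter, and Tables 2 and 8 have no exit-site item. Section 4.2 describes the exit route thus: "The catheter end is then removed through the skin away from the wound edge and secured". Section 11.1.1 puts the exit point on the lateral side of the stump. Section 5.4 cites the 2008 CDC definition of surgical site infection and Section 12.1.5 the 2021 one; neither section says whether the exit site is included. An exit-site infection that starts after day 7 and after discharge, and is not classed as surgical site infection, could therefore go unrecorded.

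**The case against.** The strongest reply is that the protocol, read as a whole, already treats catheter events as SARs. Table 7 lists placement in its IMP column, the SAE form records the IMP or the trial intervention, and the longer window refers to trial treatment, which Sections 9.5.2 and 14.1 define as a catheter with an infusion. On that reading, placement-related events stay reportable to the end of follow-up. This is a fair reading, and some sites would adopt it. But it has to override the definition in Table 3, and a site deciding whether to send a form will look there first. What stands is that the fault is inconsistent wording rather than a deliberate exclusion.

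A reader might go further and infer that late catheter harms go uncounted and that the benefit-risk conclusion is biased towards the catheter. The protocol does not support that. Several outcomes run past day 7 in both arms, SAEs that start inside the window are followed to resolution, and other adverse events have no stated end date. A catheter that cannot be removed would ordinarily come to light at removal, on day 5 or before. Exit-site infection can occur only in the catheter arm, so any loss would fall on that arm, but no rate of late events is given and Section 4.1 describes side effects of these catheters, including infection, as very uncommon. A material bias is not shown.

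It is also true that nothing in the protocol obliges SAE reporting to run to day 30, and that the trial is classed as no riskier than standard care. The remedy therefore need not move the general day-7 limit.

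**Conclusion.** The point holds as a contradiction in the safety-reporting rules. SAE reporting ends 2 days after planned removal, and the only later window is tied by Table 3 to the drug, while Sections 13.2 and 13.3 and Table 7 treat the catheter as a source of reportable harm. On the literal reading, a serious catheter-related event that starts after day 7 and is not attributed to the drug has no SAE or SAR route and does not enter the SAR-based reports.

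What is lost for most such events is prompt reporting and attribution to the catheter, since many would leave a trace in another outcome. Complete loss is plausible mainly for an exit-site infection that arises after both day 7 and discharge. The number cannot be computed from the protocol and may be small. The conclusion rests on taking Table 3 at its word and on the general day-7 limit applying to the trial-specific SAEs. The primary outcome is not affected. The passages should be reconciled because the ambiguity is plain and cheap to remove.

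**What to change.** Reconcile Sections 13.1, 13.3 and 13.5.1 so that the SAR definition, the decision column of Table 5 and the window to the end of follow-up all expressly cover events related to catheter placement as well as to the IMP. State in Section 13.2 which window applies to exit-site infection.

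Add one item to the existing 30-day note review and to Table 2: exit-site infection or other catheter complication, recorded separately from surgical site infection.

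While Section 13.5.1 is open, correct its page reference for the end of follow-up: the contents list places Data Management on that page.

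The cost is protocol wording, a few more SAE forms and one extra CRF item. No new visit is needed.

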13.5.2 The CTR Responsibilities

Following the initial report, all SAEs should be followed up to resolution wherever possible, and further information may be requested by the CTR. The most recent form can be updated with new information. Once an SAE is received at the CTR, it will be evaluated by staff at the CTR and sent to the CI (or their delegate) for an assessment of expectedness. Investigator reports of suspected SARs will be reviewed immediately and those that are identified as SUSARs are reported to the MHRA, Main Ethics Committee.

13.6 SUSAR Reporting

Cardiff University is undertaking the duties of trial Sponsor and has delegated to the CTR the responsibility for reporting SUSARs and other SARs to the regulatory authorities (NCAs and relevant ethics committees) as follows:

- SUSARs which are fatal or life-threatening must be reported to the MHRA and REC within 7 calendar days of receipt at the CTR
- SUSARs that are not fatal or life-threatening must be reported to the MHRA and REC within 15 days of receipt at the CTR. If report is incomplete, then additional follow-up information should be reported within a further 8 calendar days of submitting the initial report.

13.7 Safety Reports

A list of all SARs (expected and unexpected) will be reported annually to the MHRA REC and trial sponsor in the form of a Development Safety Update Report (DSUR). This report must be submitted within 60 days of the anniversary of the MHRA CTA approval date. The CTR will report a list of all SARs (expected and unexpected) and any other safety recommendations to all PIs annually throughout the course of the trial. This frequency may be reviewed and amended, as necessary. This reporting will be done via the Investigator safety report (ISR).

13.8 Contraception and Pregnancy

13.8.1 Contraception

Although there is no evidence of untoward effects of Levobupivacaine, Ropivacaine or Bupivacaine in human pregnancy, animal studies have evidenced harm of using Levobupivacaine or Bupivacaine when administered in pregnancy. People of childbearing potential entering this trial must therefore agree to use a highly effective method of contraception preferably with low user dependency for at least one week postoperatively. A highly effective method of contraception is considered as having a failure rate of less than 1%. Some acceptable contraception methods are listed below:

- combined (oestrogen and progestogen containing) hormonal contraception associated with inhibition of ovulation:
 - \circ oral
 - o intravaginal
 - o transdermal
- progestogen-only hormonal contraception associated with inhibition of ovulation
 - \circ oral
 - o injectable
 - implantable*
- intrauterine device (IUD)*
- intrauterine hormone-releasing system (IUS)*
- bilateral tubal occlusion*
- vasectomised partner*
- sexual abstinence defined as refraining from heterosexual intercourse during the entire period of risk associated with the trial treatments.

N.B. periodic abstinence (calendar, symptothermal, post-ovulation methods), withdrawal (coitus interruptus), spermicides only, and lactational amenorrhoea method are not acceptable methods of contraception.

*These contraception methods are considered to be low user dependency.

13.8.2 Pregnancy Reporting while Participating in the Trial

Pregnancy, or the pregnancy of a partner occurring while participating in the trial, is not considered an SAE, however, a congenital anomaly or birth defect is. Other cases (e.g., termination of pregnancy without information on congenital malformation, and reports of pregnancy exposure without outcome data) should not normally be reported as such. When pregnancy occurs in a trial, either in a female participant or the female partner of a male participant, this should be followed up until at least the end of pregnancy, whether that is a live birth, abortion etc. Without follow-up of the pregnancy, it would not be possible for the CTR to know if a congenital anomaly or birth defect occurred, and therefore if there was an SAE that must be included in the safety evaluation of the IMP. Information on a pregnancy in a trial participant will be captured on the CTR Pregnancy Report Form supplied to sites by the CTR.

Sites should report pregnancy occurring within SAE reporting periods stipulated in the trial protocol. Congenital anomalies or birth defects are considered an SAE and so these events must also be reported to the CTR on a trial-specific SAE form. Congenital anomalies or birth defects related to the IMP and unexpected with respect to the IMP Reference Safety Information (RSI) must be submitted by the CTR within expedited SUSAR time frames (7 or 15 days) to the MHRA, relevant REC and the drug manufacturer of the IMP (to comply with any contractual agreement).

13.9 Urgent Safety Measures (USMs)

An urgent safety measure is an action that the Sponsor, CI or PI may carry out to protect the subjects of a trial against any immediate hazard to their health or safety. Any urgent safety measure relating to this trial must be notified to the MHRA and Research Ethics Committee immediately by telephone, and in any event within 3 days in writing, that such a measure has been taken. USMs reported to the CTR will be handled according to CTR processes.

[figure not shown]

Figure 1 Adverse event reporting flow chart

14. Statistical considerations

14.1 Randomisation

Participants will be allocated via covariate minimisation on the planned level of amputation (BKA vs. TKA vs. AKA), type of anaesthesia (general vs. neuraxial), preoperative pain score, and recruitment site. Allocation will be in a 1:1 ratio to either active treatment (placement of a PNC with a postoperative infusion of local anaesthetic in addition to standard anaesthetic and postoperative analgesia) or control (standard anaesthetic and postoperative analgesia alone). A random element will be added to the (otherwise strictly deterministic) minimisation algorithm to reduce predictability [REF: www.bmj.com/content/330/7495/843].

Computerised web-based remote randomisation (available 24 hours a day) will be used. A 9am-5pm telephone back up will be available for use if the online system does not work or the site has problems accessing the online website. A detailed randomisation plan will be finalised and signed off prior to any participant being randomised.

14.2 Blinding

The PLACEMENT trial does not use blinding.

14.3 Sample size

'Good' pain control is defined as \leq 3 on a 0-10 NRS (66). Feasibility trial participants in the control arm reported 'freedom from pain' (defined as NRS \leq 3, or pain \leq 'mild' on a 4-point Verbal Rating Scale) 61.7% of the time in the first 5 postoperative days. Treatment arm participants reported 'freedom from pain' 76.8% of the time, a relative improvement of 24.5%. Using a more conservative (but still clinically important) relative improvement of 20% between arms results in a sample size of 299 participants per arm for 90% power when using a two-sample test for proportions with two-sided 5% alpha. In our feasibility trial, 45 of the 49 participants (92%) provided primary outcome data (defined as a participant providing outcome data for pain in >50% of possible timepoints). To account for this, a sample size of 650 is required.

14.4 Missing, Unused and Spurious Data

Complete case analysis will be used for the primary analysis. We will employ multiple imputation of missing outcome data as a sensitivity analysis and report the impact on the treatment effect alongside the complete case analysis. Further detail will be provided in the Statistical Analysis Plan (SAP).

